### 5.7.1. Analysis of Adverse Events

In general, the primary focus of AE reporting will be on TEAEs presented in each of the study period, specifically the double-blind and open-label period. Pre-treatment and post-treatment AEs will be provided separately.

If an AE date/time of onset (occurrence, worsening, or becoming serious) is incomplete, an imputation algorithm will be used to classify the AE as pre-treatment, treatment-emergent, or post-treatment. The algorithm for imputing date/time of onset will be conservative and will classify an AE as treatment-emergent unless there is definitive information to determine pre-treatment or post-treatment status. Details on classification of AEs with missing or partial onset dates are provided in [Section 6.4](#).

Adverse event incidence tables will present the number (n) and percentage (%) of patients experiencing an AE by SOC, HLTG (when applicable), HLT (when applicable), and PT. Multiple occurrences of the same event in the same patient will be counted only once in the tables within a treatment phase. For tables presenting severity of events, the worst severity will be chosen for patients with multiple instances of the same event. The denominator for computation of percentages is the safety population within each treatment group.

The table of all TEAEs presented by SOC and PT will be sorted by the internationally agreed SOC order and decreasing frequency of PTs within SOCs (in the alirocumab group). This will define the presentation order for all other tables by SOC and PT, unless otherwise specified. The tables of AEs by SOC, HLTG, HLT and PT will be sorted by the SOC internationally agreed order and the other levels (HLTG, HLT, PT) will be presented in alphabetical order, unless otherwise specified.

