### Analysis

Treatment-emergent and post treatment AEs in both the double-blind and open-label study periods will be summarized in incidence tables by (at least) SOC (sorted by internationally agreed order), and PT (sorted by decreasing frequency, and the number (n) and percentage (%) of patients experiencing an AE). The high level group term and high level term can be added in alphabetical order, as applicable. Multiple occurrences of the same event in the same patient will be counted only once in the tables within the TEAE period. Data conventions for missing or partial AE dates will be addressed in the SAP. The denominator for computation of percentages is the safety set within each treatment group.

Adverse event incidence tables will be provided by treatment group for all types of TEAEs: all TEAEs, all TEAEs of interest (defined with a PT or a pre-specified grouping), TEAE by severity, all treatment-emergent SAEs, and all TEAEs leading to permanent treatment discontinuation.

If any clinically significant signal is detected and further characterization is needed, or for AEs of clinical interest, selected TEAEs will be analyzed using a time-to-event approach (Kaplan Meier methodology) to account for the differential exposure time in all patients. Time from the first dose of the investigational study drug to the first occurrence of the event will be calculated (only the first event will be counted). Patients without any event will be censored at the end of the TEAE period.

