### **1.2.3. Modifications from the Statistical Section of Protocol Amendment 3**

This SAP is based on Protocol R727-CL-1628 Amendment 3. The following modification from the protocol amendment 3 is made in this SAP:

- The analysis for new onset of diabetes in Protocol Section 9.3.3 (Adverse Events of Special Interest) is deleted since the definition for new onset of diabetes is not appropriate for this short-term study. Instead, the analysis for diabetes mellitus or diabetic complications is added in [Section 4.7.1.2](#).

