#### ***Analysis of Adverse Event in the Open-Label Period***

For open-label period, summary of adverse events as described for the double-blind period will be used.

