## 7. TIMING OF STATISTICAL ANALYSES

Efficacy and safety analyses for this study will be performed in two steps, specifically for patient data collected up to the time the last patient completes efficacy assessments at week 12 (step 1 consisting of the double-blind period) and at the end of the study (step 2 for the open-label period). No formal interim analysis for efficacy is planned since analyses of primary and key secondary efficacy endpoints will be final at the time of first-step analysis. Therefore, no multiplicity adjustment for multiple analyses is needed (see [Section 5.6.3](#)). The timing for patient data to be reported is defined below for each step:

- First-step: efficacy analyses up to week 12 and interim safety analysis
  - This analysis will be conducted on all randomized patients when all patients will have all their lipid data up to week 12 analysis window collected and validated.
  - The efficacy analyses will be performed up to week 12 time point. Analyses of endpoints up to week 12 time point will correspond to the final analyses for these endpoints. Analysis of lipid parameters beyond week 12 will be descriptive.
  - The safety analyses will be performed on all safety data (double-blind and open-label) collected up to the common cut-off date. For this analysis, the common cut-off date is defined as date of the last week 12 visit.
- Second-step: final analysis
  - This analysis will be conducted at the end of the study and will consist of the final analysis of efficacy data at time points beyond the week 12 time point and final safety analysis.

Individuals involved in the first-step analysis of the study will not be involved in the conduct of the study afterwards; individual patient identification will not be released to anyone who is directly involved in the conduct of the study. The first-step analysis process, the measures used to protect the blind and the integrity of the study, the communication plan, and the confidentiality agreement will be described in a separate document. The results of the first analysis will not be used to change the conduct of the ongoing study in any aspect. The first analysis will be used for the submission dossier to health authorities.

Analyses methods and conventions described in the other sections of this SAP will be applied for all analyses as applicable. The following additional rules will apply for analyses performed at first-step analysis:

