- Any lipid assessments within analysis windows up to week 12 will be taken into account (may include few unscheduled lipid data soon after the cut-off date).

- Patients without end of treatment visit (double-blind or open-label) performed at the time of the cut-off date will be considered as ongoing and exposed up to the cut-off date. Therefore:
  - Patients who did not complete the respective treatment period nor prematurely discontinued the study treatment at cut-off date will be analyzed as “ongoing” in the disposition summary.
  - Their TEAE period and treatment period will end at the cut-off date.
  - Their treatment duration will be derived by considering date of cut-off as last injection date.
- Analyses of number of injections, mean injection frequency, percentage of days with under/above-planned dosing and compliance will be performed up to the last injection reported in the e-CRF up to the cut-off date.
- AEs occurring, worsening or becoming serious after the cut-off date will not be included in the analyses. However, any available outcome before database lock, regardless of timing in relation to the cut-off date, of an adverse event starting prior to the cut-off date will be taken into account. Medications, treatment discontinuations/completions and deaths occurring after the cut-off date will not be included in the analyses.
- Post-treatment period, post-study period are not applicable for ongoing patients. Analyses of post-treatment AEs, post-study deaths and post-treatment medications will be performed for patients who either completed or prematurely discontinued the treatment before or at the cut-off date.
- Analysis of status at last study contact and proportion of patients with insufficient follow-up will be provided for patients who either completed or prematurely discontinued the treatment before or at the cut-off date.

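### First-step open-label adverse-event percentages pool follow-up from 1 day to about 20 weeks, and the protocol's time-to-event method for unequal exposure is not carried into the SAP

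*SAP*

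**What the plan says.** **Denominator.** SAP 5.7.1 prescribes patient counts and percentages: "The denominator for computation of percentages is the safety population within each treatment group". That sentence names the safety population. The open-label denominator comes from SAP 5.7, which presents open-label safety on the open-label population, and from SAP 3.6, which admits anyone with at least one full or partial open-label dose. The method carries over: "For open-label period, summary of adverse events as described for the double-blind period will be used".

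**Cut-off.** SAP 7 says of the first step: "The safety analyses will be performed on all safety data (double-blind and open-label) collected up to the common cut-off date". It adds: "For this analysis, the common cut-off date is defined as date of the last week 12 visit". For patients with no end-of-treatment visit by then: "Their TEAE period and treatment period will end at the cut-off date". Events starting after the cut-off are excluded for everyone. On use: "The first analysis will be used for the submission dossier to health authorities".

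**Period at risk.** SAP 4.7.1 runs the open-label treatment-emergent period from the first open-label injection to 70 days after the last.

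**Unequal exposure.** Protocol 10.4.4.1, after a signal or for events of clinical interest, says: "selected TEAEs will be analyzed using a time-to-event approach (Kaplan Meier methodology) to account for the differential exposure time in all patients". Patients without an event are censored at the end of the treatment-emergent period. SAP 5.7.1 has no Kaplan-Meier, person-time or exposure-adjusted event rate. Its nearest items, events per double-blind injection and time to first reaction, cover injection-site reactions only. SAP 1.2.3 introduces its departures with "The following modification from the protocol amendment 3 is made in this SAP" and lists only the new-onset-diabetes analysis.

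**The concern.** Open-label dosing starts at week 12 and the cut-off is the last week 12 visit, so the most recent enrollees have almost no open-label time when the submission tables are made. Each still counts as a full unit in the denominator, and events they have later are not in the numerator. The percentage is then a mixture over very different follow-up times. It depends on how fast the last patients enrolled as well as on the event rate.

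At stake is the reading of the open-label safety tables in the dossier. A reader would naturally take such a percentage as the risk over the open-label period, and for that purpose it is too low. The protocol anticipated unequal exposure and named a method for it. The SAP is silent on the method and does not say that it was dropped.

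**Working it through.** The plan gives no open-label event rate and no count of truncated patients, so there is no stated figure to reproduce.

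**Follow-up at the cut-off**

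- First open-label dose on day 85, last on day 155 (Protocol 5.1). Full open-label treatment-emergent period: (155 − 85) + 70 = 140 days = 20 weeks.
- A patient whose week 12 visit and first open-label dose fall on the cut-off date has 1 day.
- A week 12 visit in the 12 weeks before the cut-off leaves an incomplete open-label treatment phase. One in the 20 weeks before it leaves an incomplete treatment-emergent period.
- The double-blind treatment-emergent period ends no later than the day before the first open-label dose. Every week 12 visit is on or before the cut-off, so double-blind follow-up is essentially complete. A possible exception is the 70-day tail of early discontinuers who never enter open-label.

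**Size of the understatement**

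Assumptions, none of them given in the documents: all 74 patients enter open-label; 54 are fully observed; the other 20 have open-label time t_i at the midpoints of 20 equal steps over (0, W) weeks; the hazard is constant. As an illustrative rate I use a 12-week risk of 7.2%. Protocol 3.2.2 reports that figure for injection-site reactions without a stated duration, so treating it as a 12-week risk is also an assumption.

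- Weekly hazard: h = −ln(1 − 0.072)/12 = 0.00623.
- True risk over horizon H: R = 1 − exp(−hH), which is 7.2% at H = 12 and 11.7% at H = 20.
- Expected crude percentage: [54R + Σ(1 − exp(−h·min(H, t_i)))]/74.

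Example, W = 12: the 20 late patients have 20 × 6 = 120 weeks in total and 0.73 expected patients with an event. At H = 20 the crude value is (54 × 0.1171 + 0.73)/74 = 9.5% against 11.7%. Mean follow-up is (54 × 20 + 120)/74 = 16.2 weeks.

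| W (weeks) | H = 12: truncated patients | crude vs 7.2% | relative shortfall | H = 20: truncated patients | crude vs 11.7% | relative shortfall |
|---|---|---|---|---|---|---|
| 12 | 20 | 6.2% | 13% | 20 | 9.5% | 19% |
| 20 | 12 | 6.6% | 8% | 20 | 10.2% | 13% |
| 26 | 9 | 6.8% | 6% | 15 | 10.5% | 10% |
| 52 | 5 | 7.0% | 3% | 8 | 11.1% | 5% |

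In patients, the shortfall is 74 × (R − crude): 0.2 to 0.7 on 12 weeks and 0.4 to 1.6 on 20 weeks.

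**Sensitivity (12-week horizon)**

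- Number truncated: letting it run from 5 to 33 with uniform exposure gives about 3% to 22%. The upper end, 74 − 41 = 33, takes 41 as 75% of the original 54, and supposes that all 33 others had their week 12 visit within 12 weeks of the cut-off. It is an extreme.
- Event timing: if all risk falls in the first 2 weeks, the shortfall is about 1% to 4% for 10 to 33 truncated patients.
- Remedy: with a true 12-week risk of 20%, simulated Kaplan-Meier estimates average 20.0% with 10, 20 or 33 truncated patients. The crude percentage averages 18.7%, 17.4% and 15.7%.

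**Can the exposure table correct for this?** Not by itself. SAP 7 takes the cut-off as an ongoing patient's last injection date, and SAP 4.5 adds 14 days. A patient first dosed on the cut-off date is credited with (0 + 14)/7 = 2.0 weeks of exposure against 1 day of event observation.

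**The case against.** **The effect is small and not hidden.** In the illustration it is under two patients. SAP 7 calls the first step an interim safety analysis, SAP 4.4 counts patients still ongoing in open-label, SAP 4.5 tabulates exposure from 1 day upward, and the second step gives the final safety analysis. All of this stands. It limits the importance of the point, but a reader still cannot convert the percentages into a risk over a defined time.

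**The protocol method is conditional.** Protocol 10.4.4.1 itself makes n (%) the standard table and reserves Kaplan-Meier for selected events. SAP 6.4 still has a date rule headed partly for survival analysis. So silence in SAP 5.7.1 is not proof of removal, and a reader who inferred that the protocol requires time-to-event analysis of every table would be going too far. What stands is that the SAP neither specifies the method nor declares its absence.

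**Direction against the double-blind rates.** A reader might infer that open-label rates must fall below the double-blind rates and so always flatter the drug. The documents do not support that. The double-blind period is about 12 weeks and the full open-label period about 20. In the scenarios above the crude open-label figure is 9.5% to 11.1%, above the 12-week risk of 7.2%. This assumes that completers are followed to week 32. Patients who enter another lipid-lowering study skip that call, and their share is not given.

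**Conclusion.** The point holds for the first-step open-label tables. Their percentages mix follow-up from 1 day to about 20 weeks and sit below the full-period open-label incidence. Under a constant hazard, 54 fully observed patients and 20 late enrollees spread evenly over 12 to 52 weeks, the understatement is about 5-19% relative on 20 weeks and 3-13% on 12 weeks. It is smaller if events cluster early. Enrolment pace, event timing and roll-over to another study are not in the documents, so these are illustrations.

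A reader might go on to infer that alirocumab event rates in general come out too low. They do not: the alirocumab-versus-placebo comparison rests on essentially complete double-blind follow-up, and the affected tables are uncontrolled and descriptive. The undeclared gap between Protocol 10.4.4.1 and SAP 5.7.1 stands whatever the size of the effect. This is a worthwhile, inexpensive improvement and does not threaten the trial's conclusions.

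**What to change.** 1. In SAP 5.7.1, restore the conditional Kaplan-Meier analysis from Protocol 10.4.4.1, or list its removal in SAP 1.2.3.
2. In SAP 5.7.1 and SAP 7, add beside n (%) in the first-step open-label tables one of the following:
   - Kaplan-Meier incidence at a stated time from the first open-label injection, censoring ongoing patients at the cut-off; or
   - events per patient-year, using actual observation time and not the exposure duration that adds 14 days.

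   Do this for any treatment-emergent event, serious events, events leading to discontinuation and each special-interest grouping, and show the number still ongoing. This list goes beyond the protocol's conditional scope and is a recommendation.
3. State the open-label population as the denominator for open-label tables. Correct the pointer in SAP 5.7, which sends the reader to Section 3.3 (the antibody set) when the definition is in Section 3.6.

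Cost: SAP wording and a few extra tables from data already collected. The downside is wide intervals, because events will be few.

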#### *Analysis of all treatment-emergent adverse events*

The following TEAE summaries will be generated:

- Overview of TEAEs, summarizing number (%) of patients with any
  - TEAE;
  - Serious TEAE;
  - TEAE leading to death;
  - TEAE leading to permanent treatment discontinuation.
- All TEAEs by primary SOC, HLTG, HLT, and PT
- Number (%) of patients experiencing common TEAE(s) presented by primary SOC, HLT and PT (HLT incidence  $\geq 5\%$  in any treatment group), sorted by SOC

internationally agreed order and by alphabetic order for the other levels (HLT and PT);

- All TEAEs by primary SOC and PT, sorted by the internationally agreed SOC order and by decreasing incidence of PTs within each SOC (in the alirocumab group).
- All TEAEs by treatment group regardless of relationship in one column and, in the same table a second column with TEAEs related to alirocumab according to investigator's opinion by primary SOC, HLT, HLT and PT;
- All TEAEs by maximal severity (i.e., mild, moderate or severe), presented by primary SOC and PT, sorted as defined above;

#### ***Analysis of all treatment emergent serious adverse event(s)***

- All serious TEAEs by primary SOC, HLT, HLT, and PT and by SOC/PT; Patient listings of serious TEAEs will be provided for the report appendix.
- All serious TEAEs by treatment group regardless of relationship in one column and in the same table a second column with TEAEs related to alirocumab according to investigator's opinion, by primary SOC, HLT, HLT, and PT;

#### ***Analysis of all treatment-emergent adverse event(s) leading to treatment discontinuation***

- All TEAEs leading to permanent treatment discontinuation, by primary SOC, HLT, HLT, and PT and by SOC/PT; Patient listings of TEAEs leading to permanent treatment discontinuation will be provided for the report appendix.

#### ***Analysis of groupings of adverse events including selected adverse events of special interest***

- All grouping of TEAEs including adverse events of special interest, as listed in [Section 4.7.1.2](#), will be presented by SMQ/CMQ and PT (when selection is based on SMQs/CMQs) and by SOC and PT (when selection is based on the e-CRF tick box or HLT/HLT). The summaries will be sorted by decreasing incidence of PT within each SOC/SMQ (in the alirocumab group).
- All TEAEs within diabetes grouping will be analyzed overall and according to the diabetic status at baseline.

The following variables will also be tabulated for the local injection site reactions TEAEs:

- Intensity of the event (mild, moderate, severe);
- Number of events divided by the number of double-blind study treatment injections received;

- Time from first study treatment injection (double-blind or open-label depending on the analysis) to first injection site reaction;
- Description of the highest intensity of each symptom recorded in the specific e-CRF page with table and bar chart.

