All patients who meet the inclusion criteria and none of the exclusion criteria will enter the 12-week double-blind treatment period. The first injection of double-blind study drug will occur on day 1 (baseline), and the last injection of double-blind study drug will occur on day 71 (week 10).

Following the completion of the 12-week double-blind treatment period, all patients will enter a 12-week open-label treatment period. The first injection of open-label alirocumab will occur on day 85 (week 12) and the last injection of open-label alirocumab will occur on day 155/week 22. After completion of the 12-week open-label treatment period, all patients who have successfully completed this study may have the opportunity to participate in an additional lipid-lowering clinical trial.

---

Study Duration	This is a 24-week study, excluding the optional 4-week run-in period and the 2-week screening period.
-----------------------	---

Population	The study population will consist of male and female patients, $\geq 18$ years of age diagnosed with HoFH.
-------------------	--

**Sample Size:** Approximately 74 patients

**Target Population:** Males and females  $\geq 18$  years of age diagnosed with HoFH, except patients known to have null/null mutations in both LDLR alleles.

---

Treatment(s)	
Study Drug	Alirocumab 150 mg SC every 2 weeks from day 1 through week 12 (end of double-blind treatment period, last double-blind injection at week 10).
Dose/Route/Schedule:	Regardless of treatment assignment in the double-blind treatment period, all patients will receive open-label alirocumab 150 mg SC Q2W starting at week 12 and continuing through week 24 (last injection in the open-label period at week 22).
Reference Drug	Placebo SC Q2W

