## 2. INVESTIGATING PLAN

### 2.1. Study Design and Randomization

This is a randomized, double-blind, placebo-controlled, parallel-group study to evaluate the efficacy and safety of alirocumab in patients with HoFH.

Approximately 74 patients will be randomized in a 2:1 ratio to receive either alirocumab 150 mg SC Q2W or matching placebo in the double-blind treatment period. Randomization will be stratified by apheresis treatment status (Yes/No).

The study will consist of up to 5 periods: an optional 4-week run-in period (for patients whose background medical LMT regimen or apheresis schedule and/or apheresis settings have not been stable prior to screening), a 2-week screening period, a 12-week double-blind treatment period, and a mandatory 12-week open-label treatment period during which all patients will receive alirocumab. Patients not continuing on to another lipid lowering study will undergo an 8-week follow-up period.

The analyses will be conducted in 2 steps. The first analysis will be conducted as soon as all patients have been randomized and all data through week 12 (double-blind period) have been collected and validated; this will consist of the final analysis of the double-blind primary and secondary efficacy endpoints. The safety analysis will be performed on all safety data collected and validated at the time of the first-step analysis database lock. Since the double-blind primary efficacy measure data collection will have been concluded at the time of this first analysis, the significance level for the study remains at 0.05. This first analysis may be used for the submission to health authorities or other interested parties.

The second analysis will be performed with the data from the open-label treatment period and will consist of the final analysis for the safety and efficacy measures beyond week 12 time point.

The results of the first analysis will not be used to change the conduct of the ongoing study in any aspect. Individuals involved in the first-step analysis of the study will not be involved in the conduct of the study afterwards; individual patient identification will not be released to anyone who is directly involved in the conduct of the study. The first-step analysis process, the measures used to protect the blind and the integrity of the study, the communication plan, and the confidentiality agreement will be described in a separate document.

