## **5.7. Analysis of Safety Data**

The summary of safety results will be presented separately for the double-blind and open-label period. The double-blind period will be presented by treatment groups (alirocumab, placebo) on the safety population ([Section 3.2](#)). The open-label period will be presented by all patients and by treatment group of the double-blind period (i.e., alirocumab, placebo) on the open-label population ([Section 3.3](#)). No formal inferential testing will be performed for either period. Summaries will be descriptive in nature. All summaries of safety results described below will be presented for each period respectively, unless otherwise noted.

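### The injection-site-reaction rate keeps its double-blind denominator when the summary is reused for the open-label period

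*SAP*

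**What the plan says.** SAP 5.7.1, under groupings of adverse events, lists four variables for treatment-emergent local injection site reactions. The second is the per-injection rate: "Number of events divided by the number of double-blind study treatment injections received". The third is "Time from first study treatment injection (double-blind or open-label depending on the analysis) to first injection site reaction", which is worded for either period.

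Two statements carry these summaries into the open-label period. SAP 5.7 sets the general rule: "All summaries of safety results described below will be presented for each period respectively, unless otherwise noted". The paragraph on open-label adverse events after SAP 5.7.1.1 adds: "For open-label period, summary of adverse events as described for the double-blind period will be used". Neither supplies a different denominator for the rate.

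The open-label results are to be shown for all patients and by double-blind treatment group (SAP 5.7). SAP 2.1 describes that period as "a mandatory 12-week open-label treatment period during which all patients will receive alirocumab". SAP 4.5 defines each patient's number of open-label injections as an exposure variable, but the reaction rate does not refer to it. For the first-step analysis, SAP 7 says: "The safety analyses will be performed on all safety data (double-blind and open-label) collected up to the common cut-off date".

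**The concern.** The rate names its denominator explicitly, and the denominator belongs to one period. When the summary is rerun for the open-label period, the numerator moves to open-label events and nothing moves the denominator. The neighbouring item shows that the list was meant to serve both analyses, so this looks like one item that was not adapted.

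A rate per injection is meaningful only if the events counted could have followed the injections counted. In the former-placebo column the mismatch is one of substance: reactions during those patients' first alirocumab exposure in the trial would be set against injections that were all placebo.

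Local injection site reactions are an adverse event of special interest (SAP 4.7.1.2). The open-label period exists to add safety data in a rare population (Protocol 5.1). The first-step output, which includes open-label data still accruing, goes into the submission dossier (SAP 7).

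**Working it through.** The plan states no reaction rate and no injection total, so there is no figure to reproduce. The check is a count of planned injections and a ratio.

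**Inputs**
- Double-blind dosing every 2 weeks, day 1 to day 71 (Protocol synopsis): (71 − 1)/14 + 1 = 6 planned injections.
- Open-label dosing every 2 weeks, day 85 to day 155 (Protocol synopsis): (155 − 85)/14 + 1 = 6 planned injections.
- Size and allocation (SAP 2.1): "Approximately 74 patients will be randomized in a 2:1 ratio to receive either alirocumab 150 mg SC Q2W or matching placebo". The placebo share is 74/3 = 24.7, about 25 patients.

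**Formula.** Let E be open-label reactions, L open-label injections and D double-blind injections in the same patients. The literal rate is E/D and the matched rate is E/L. Their ratio, literal over matched, is L/D.

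**Full adherence.** If all 74 patients enter the open-label period, D = L = 74 × 6 = 444 and the ratio is 1.0. About 25 × 6 = 150 of the 444 double-blind injections (34%) would be placebo, and all 150 in the former-placebo column. This composition does not enter L/D; only the counts do.

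**Unequal counts** (mean injections per patient; all values are assumptions)

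| Double-blind | Open-label | Literal / matched |
|---|---|---|
| 6 | 5 | 0.83 |
| 6 | 4 | 0.67 |
| 6 | 3 | 0.50 |
| 5.5 | 6 | 1.09 |

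The error can go either way: short open-label exposure understates the rate, and missed double-blind doses overstate it.

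**First-step cut-off.** The cut-off is the date of the last week 12 visit (SAP 7). The sixth open-label injection falls 155 − 85 = 70 days after week 12. Anyone who reached week 12 less than about 10 weeks before the cut-off therefore cannot have all six. The documents do not say how many patients this would be. Assume they have a mean of 3 open-label injections, that everyone else has 6, and that all 74 have 6 double-blind injections:

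| Patients mid open-label | L | L/D | Understatement |
|---|---|---|---|
| 8 | 66 × 6 + 8 × 3 = 420 | 420/444 = 0.946 | about 5% |
| 15 | 59 × 6 + 15 × 3 = 399 | 399/444 = 0.899 | about 10% |

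**The case against.** The best defence is that reuse of a summary means adaptation. SAP 5.7 presents summaries for each period respectively. SAP 5.7.1 also sets the denominator for adverse event percentages as the safety population, yet open-label percentages are clearly meant to use the open-label population. A careful programmer would change the injection count in the same way. The analogy fails on one point: SAP 5.7 itself names the open-label population as the replacement for the safety population, and nothing names a replacement for double-blind injections.

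A second defence is that the word double-blind is itself the exception that SAP 5.7 allows for, so no open-label rate is intended. That is possible, but the open-label paragraph makes no exception, and the rate would then be missing for the period in which everyone receives alirocumab. The SAP would still have to say so.

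The objections to size largely stand. Planned counts are equal, the rate is descriptive with no formal test, and incidence, intensity and time to first reaction do not use this denominator. Three stronger readings are tempting and not supported:

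- **A several-fold error.** A patient with one or two open-label injections would show 1/6 or 2/6 of the matched rate. The SAP presents safety results by group and overall, and plans no analysis of patients who are mid-treatment.
- **Many patients with partial exposure at the first step.** The documents give no such count. They suggest that a majority would be past their last planned dose. About 75% of the initial 54, roughly 40, had reached week 12 by October 2018 (SAP 2.2). The amended protocol carries an approval stamp of 4 January 2019. Patients added after that could not reach week 12 before late March 2019, more than 10 weeks after the end of October.
- **Placebo injections in the denominator distort the number by themselves.** They make the ratio hard to interpret, but only unequal counts change its value.

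**Conclusion.** The point holds as a definition that is wrong as written, with a modest effect. Followed literally, the SAP divides open-label reactions by double-blind injections. The resulting rate is correct in value only when the two counts agree, as they do at full adherence (6 and 6). It departs from the matched rate through missed doses, early discontinuation, or partial open-label exposure at the first-step cut-off.

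The overall understatement of about 5 to 10% at the first step rests on an assumed 8 to 15 of 74 patients mid open-label with a mean of 3 injections. At the second-step analysis only missed doses or discontinuation could move the rate. The double-blind rate is correctly defined, so the alirocumab-versus-placebo comparison is untouched. No efficacy result or error rate is involved.

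**What to change.** In SAP 5.7.1, replace the rate item with: *Number of events divided by the number of study treatment injections received in the respective period (double-blind or open-label depending on the analysis)*.

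No separate cut-off clause is needed. The additional first-step rules in SAP 7 already count injections up to the last one recorded by the cut-off date.

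If the sponsor intended no open-label rate, the item should say that it applies to the double-blind period only.

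The cost is one phrase in the SAP. The open-label injection count is already derived under SAP 4.5, so no new data or variable is required.
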